8.3 Definitions of analysis sets

The full analysis set (FAS) includes all randomized subjects who received at least 1 dose of IP (investigational product) and have a non-missing HbA1c value at week 24. This analysis set will be used in both efficacy and safety analyses.

The Completer Analysis Set (CAS) includes subjects in FAS who completed IP and have a non-missing HbA1c value at week 24.

In all analysis sets, unless specified otherwise, subjects will be analyzed according to the ITT principle.

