1.3 Benefit/risk and ethical assessment

Benefit:

Evidence showed that XZK treatment by reducing LDL-C levels and TG levels significantly reduces the risk of CHD events by 45%. Therefore, for the clinical benefit of dyslipidemia patients with prediabetes , they will get expert advice and guidance of lipid management from physicians.

Potential risk:

Risk associated with Study Drug:

XZK capsule is a modernized proprietary Chinese medicine product with modern pharmaceutical technology and strict Good management practices (GMP)production management. A few mild or moderate gastrointestinal (GI) effects may occur when taking XZK, but a large number of clinical application results show that XZK capsule is safe and with few side effects [1].

Atorvastatin decrease cholesterol production in the liver by preventing the conversion of HMG-CoA to mevalonate. Common side effects to Atorvastatin include gastrointestinal (GI) effects, headache, and mild muscle pain. Rare side effect include rhabdomyolysis, dark urine, jaundice, etc.

Participants with high potential risk (meet one of the Exclusion Criteria) will not be eligible for enrollment . Moreover, we will minimize this risk by mandating adequate follow-up visit to ensure clinical assessment(e.g.CK and liver enzymes (ALT, AST)) during study participation . Local Investigator and the sponsor will also collect and report serious adverse events according to regulations. The study drug will be discontinued immediately, if any ADR occurs during the study.

Risk associated with Study Procedure:

In view of the few patients with prediabetes receive drug treatment and Statins are the most effective and acceptable drugs to treat dyslipidemia, patients may be initially hesitant to participant in this study. Previous studies have reported that XZK is effective in blood lipid reduction. We will provide the patients with pre-study education on dyslipidemia medication therapy.

Loss to follow up is another risk factor which can affect the incident rate in statistical analysis and outcome. However, this study is designed for 24 weeks short intervention and contains 5 visits with the assistance of local investigators and experienced CRO team. Therefore, we are confident to limit the loss to follow up rate.

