1.4.3. Minimizing Sources of Bias

Because treatment will be open-label, blindly tested of outcomes will be conducted by adjudicators who are unaware of treatment allocation.

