3.8. Participant Discontinuation from the study treatment

An excessive rate of participant discontinuations from either treatment or “drop-outs” from the study may render the trial non-interpretable. In this study, HbA1C data are crucial to the primary analysis and must be collected until the end of the study, even if participants are no longer taking study medication. Therefore, all efforts will be taken to

motivate participants to comply with all study procedures and to continue to be followed until the end of the trial.

Participants should be specifically asked about any possible AE or other reasons that led to their decision to withdraw from the study, and all AE information obtained should be recorded. Participants may withdraw their informed consent orally or in writing, and they are advised to withdraw informed consent in writing

The investigator and participant must discuss and determine further follow-up options. Options for follow-up are listed below, in descending order of preference:

1. Participant continues the regular study clinic visits at the investigator's site as outlined in the protocol.
2. Participant will be contacted by phone at the regular follow-up intervals.
3. Participant allows his/her general practitioner or a family relative to be contacted at the regular follow-up interval.
4. Participant will be contacted once at the end of the study.
5. Participant withdraws consent. This will be the last option and means that the participant does not agree to any kind of follow-up and specifically refuses any further contact with the investigator. This should happen only in exceptional cases. If possible by local regulations, this decision will be provided in writing. Vital status will be obtained at study end through public information according to local guidelines and as allowed by local regulations. For participants who do not agree to attend regular study visits, the investigator will encourage the participant to return to the clinic for at least one final visit in order to perform all assessments as outlined for the end of Study(EOS) visit.

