7.5 Compliance

Participants in both arms will self-administer the study the study drug at home, compliance with study intervention will be assessed at each visit. Compliance will be assessed by counting returned tablets and patient diary during the site visits and documented in the source documents and CRF.

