8.4 Efficacy analysis

8.4.1 The primary endpoints

The change value of HbA1c levels from baseline to 24 Weeks or before antidiabetic therapy initiation within 24 weeks will be analyzed using covariance(ANCOVA) model use the treatment group(XZK, atorvastatin) as the group and the baseline HbA1c as the covariate. The results will be presented as least squares means (lsmeans) with 95% confidence intervals and p-values. Model assumptions will be explored and, if necessary, appropriate transformations or non-parametric analysis techniques will be used. The primary analysis set for this analysis is the full analysis set (FAS).

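### The primary analysis set requires at least one dose, although in this open-label trial the patient knows the arm before a first dose taken at home

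*Protocol*

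**What the plan says.** Section 8.3 of the protocol puts two conditions on the full analysis set. The first is dosing: "The full analysis set (FAS) includes all randomized subjects who received at least 1 dose of IP". The second is that subjects must also "have a non-missing HbA1c value at week 24. This analysis set will be used in both efficacy and safety analyses". One set therefore serves both efficacy and safety, and section 8.4.1 names it as the set for the primary analysis. Section 8.3 defines only one other set, the completers, which is a subset of the FAS. No set of all randomised subjects is defined. The section closes with a general statement: "In all analysis sets, unless specified otherwise, subjects will be analyzed according to the ITT principle".

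Four other places decide whether the dosing condition is harmless:

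- Section 1.4.3 confines blinding to outcome assessment: "Because treatment will be open-label, blindly tested of outcomes will be conducted by adjudicators who are unaware of treatment allocation".
- Section 3.3.3 has the patient told the allocation after randomisation.
- Section 7.2 starts treatment after the day of randomisation.
- Section 7.5 places dosing outside the clinic: "Participants in both arms will self-administer the study the study drug at home".

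On follow-up, section 3.8 says that HbA1c data "must be collected until the end of the study, even if participants are no longer taking study medication".

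**The concern.** Dropping randomised subjects who never took a dose is a common rule. It is usually defended on the ground that the decision to start is unrelated to the arm, as under blinding. That defence is not available here. Patient and investigator both know the arm before the first dose, and the first dose is taken at home at least a day later. A patient who hoped for the other drug can decline to start and then leaves the primary comparison.

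Patients who decline a conventional statin need not resemble patients who decline a traditional Chinese medicine. The exclusions could differ between arms in number and in expected HbA1c change. At stake is the randomised basis of the primary comparison.

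The rule also treats similar subjects differently. Someone who stops after a single dose and returns at week 24 is analysed; someone who takes none and returns at week 24 is not. The protocol gives no reason for the difference.

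**Working it through.** **1. The plan's own figure (section 8.1).** Inputs: difference 0.3 points, SD of change 1.0, 5% significance (taken as two-sided), 80% power, 10% dropout.

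- Normal approximation: n = 2 × (1.96 + 0.842)² × 1.0² / 0.3² = 174.4, so 175 per arm. The t-test solution is 175.4, so 176.
- Dropout: 176 / 0.9 = 195.6, so 196 per arm and 392 in total.

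The stated 176 and 392 reproduce. No figure in section 8.1 is in error.

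**2. Whom the dosing condition alone removes.**

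| Subject | Week-24 HbA1c | In the FAS? | Removed by |
|---|---|---|---|
| Took at least one dose | present | yes | – |
| Took at least one dose | missing | no | week-24 condition |
| Never started | missing | no | both conditions |
| Never started | present | no | dosing condition alone |

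Only the last row is this rule's own effect. Repairing the week-24 condition would not restore these subjects.

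**3. Size of the shift.** Let f be the share of one arm's subjects with a week-24 HbA1c who are removed by this rule. Let d be the gap in mean HbA1c change between them and the dosed subjects of that arm. The mean of all subjects is then the dosed mean plus f × d, so excluding them moves the arm mean by f × d. The protocol gives neither f nor d; both are assumed. The last column is the two-sided type I error if there is no true difference and exclusion occurs in one arm only, with SE = 1.0 × √(2/176) = 0.107.

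| f | d (points) | Shift f × d | Share of 0.3 | Type I error |
|---|---|---|---|---|
| 2% | 0.3 | 0.006 | 2% | 5.0% |
| 2% | 0.5 | 0.010 | 3% | 5.1% |
| 2% | 1.0 | 0.020 | 7% | 5.4% |
| 5% | 0.3 | 0.015 | 5% | 5.2% |
| 5% | 0.5 | 0.025 | 8% | 5.6% |
| 5% | 1.0 | 0.050 | 17% | 7.6% |
| 10% | 1.0 | 0.100 | 33% | 15.5% |

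The last row is an outer bound, not an expectation. It sets f equal to the whole planned dropout and d equal to a full SD of change.

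**4. Cost of including never-starters.** Suppose a share f of the atorvastatin arm never starts and so has none of the assumed 0.3-point rise. The expected difference becomes 0.3 × (1 − f). With 176 per arm observed (normal approximation, 80.4% with no dilution):

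- f = 2%: difference 0.294, power 78.8%, and 182 per arm needed for 80%.
- f = 5%: difference 0.285, power 76.2%, and 194 per arm needed for 80%.

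Never-starters in the Xuezhikang arm would cause no such dilution under section 8.1, because that arm is assumed not to change.

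**The case against.** Several points on the other side stand.

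- **The ITT sentence is not plainly contradicted.** A reader might infer that section 8.3 claims intention to treat and then breaks it. But the sentence covers every set, including the completers, where it can only mean analysis in the arm assigned. On that reading there is no contradiction. The FAS is still a modified ITT set that omits randomised subjects.
- **Section 3.9 does not settle the matter.** Its statement on randomised cases concerns keeping records that can serve an ITT analysis. It defines no analysis set.
- **Section 1.3 does not predict arm-driven refusal.** It says that "patients may be initially hesitant to participant in this study", which concerns joining the trial, and it answers this with education before the study. It cannot be used as evidence that patients will decline an assigned drug. The one-week diary before randomisation and the handing out of drug at Visit 1 also make non-starting less likely.
- **Never-starters would not be invisible.** Sections 7.5 and 7.6 require counts of dispensed and returned drug, so their number per arm could be reported. How their HbA1c would have changed would not be shown.
- **The week-24 condition is probably the larger departure.** The protocol plans for 10% dropout, and many never-starters may have no week-24 value.
- **The magnitudes are assumptions**, and the upper values of d are strained: 1.0 is more than three times the design difference.

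None of this removes the main point. The decision to start is made with the arm known, and the protocol makes that decision a condition of entry to the primary set.

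**Conclusion.** The point holds as a defect of definition with small expected bias. The one-dose condition in section 8.3 lets entry to the primary set depend on a choice made after the arm is known, so randomisation does not protect that exclusion. If the rule removes 2% to 5% of one arm, with a gap of 0.3 to 1.0 points, the arm mean shifts by 0.006 to 0.05 points, or 2% to 17% of the design difference. The conclusion that the rule permits selection rests on the protocol's text. The size rests on assumed values of f and d, with all exclusion placed in one arm.

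A reader might go further and infer that the trial expects arm-driven refusals, or that the primary result is seriously biased. The document supports neither: it gives no non-start rate, and at low rates the effect is slight. The change is still worth making, because it is a simple edit that removes a dependence on known allocation.

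**What to change.** In section 8.3:

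1. Delete the at-least-one-dose condition from the primary efficacy set, and define that set as all randomised subjects, analysed in the arm assigned. The week-24 condition needs its own decision; removing the dosing condition does not resolve it.
2. Define a separate safety set of subjects who received at least one dose. This is needed because the FAS now serves safety as well, so dropping the condition alone would bring untreated people into the safety tables.

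In section 3.8, state that HbA1c collection off drug also covers subjects who never start. The present wording speaks of people who have stopped taking medication. Carry the same definitions into the SAP.

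The cost is a few sentences and no new visits or tests. The statistical price is a slightly diluted effect and the small loss of power shown in step 4 of the working, if some atorvastatin subjects never start.

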6.2 Serious adverse event

An AE is considered a serious AE (SAE) if it fulfills one or more of the following criteria:

- Results in death
- Is life-threatening
- Requires or prolongs hospitalization
- Is a congenital anomaly or birth defect
- Is a persistent or significant disability/incapacity
- Is another important medical event in the opinion of the investigator

The requirement or extension of hospitalization is not considered a SAE if it fulfills one or more of the criteria(see Appendix 2):

SAEs or non-serious AEs that are not study outcomes and are not expected as part of normal treatment and progression of the disease or expected with the treatment with Xuezhikang and atorvastatin, must be reported. All SAEs, all non-serious AEs leading to permanent discontinuation of study-drug treatment and non-serious AEs which the investigator considers of particular concern will be recorded on the Adverse Event Report form.

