6.4.3 Reporting of non-serious ADR

Any non-serious ADR occurs in the course of the study must be reported per the China regulation.

If any non-serious ADR occurs in the course of the study, then investigators or other site personnel should inform Luye **within 7 calendar days** when he or she becomes aware of it.

All collected adverse events will be summarised in the final study report.

Send ADR reports to Luye Pharma Group Co., Ltd , via Email: [contact] ;

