8.4.3 Safety Endpoints Analyses

Adverse events are coded by using standard terminology. Subject incidences of treatment-emergent adverse events, serious adverse events, treatment-related adverse events and adverse events leading to discontinuation will be tabulated by system organ class and preferred term for each treatment group.

Subgroup analysis of AE tables by the stratification factor, gender, and age will be performed.

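### The safety tables are tied to a set that requires a week-24 HbA1c, so treated subjects without that sample, including any who die before it, are left out

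*Protocol*

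**What the plan says.** Section 8.3 of the protocol builds the FAS from two conditions. The first is exposure: "The full analysis set (FAS) includes all randomized subjects who received at least 1 dose of IP". The second is an outcome measurement, and the same passage gives the set its use: "and have a non-missing HbA1c value at week 24. This analysis set will be used in both efficacy and safety analyses".

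One other set is defined: "The Completer Analysis Set (CAS) includes subjects in FAS who completed IP". It lies inside the FAS. No safety set is defined.

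Section 8.4.3 lists the safety output without naming a set: "Subject incidences of treatment-emergent adverse events, serious adverse events, treatment-related adverse events and adverse events leading to discontinuation will be tabulated". Section 6.4.3 promises more: "All collected adverse events will be summarised in the final study report".

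On follow-up, section 3.8 says that HbA1c data "must be collected until the end of the study, even if participants are no longer taking study medication".

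**The concern.** Whether a subject counts in the adverse event tables depends on an efficacy measurement taken at the end of treatment. A safety denominator should depend on exposure alone. Here a subject can take study drug, have a serious event, have it recorded and reported to the sponsor, and still be absent from the by-arm incidence tables because one blood sample is missing.

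Death shows this most plainly. It is the first criterion for a serious adverse event in section 6.2 ("Results in death"), yet a subject who dies before the week-24 sample can never be in the set. Adverse events leading to discontinuation are also exposed, because an event that makes someone stop treatment may also make them stop attending. That category is one of those to be tabulated.

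What is at stake is the safety comparison of XZK with atorvastatin. The trial is open-label, so the reasons for leaving may differ by arm. If they do, the tables can show a difference between arms that does not exist, or hide one that does.

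**Working it through.** **1. Which set governs the safety tables.**

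- 8.3 assigns the FAS to safety in express words.
- The completer set is narrower, so it cannot restore anyone.
- 8.4.3 names no set, so 8.3 applies.
- The intention-to-treat sentence in 8.3 governs how subjects are handled within each set. It adds nobody to a set.

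A dosed subject without a week-24 HbA1c is therefore outside every table in 8.4.3.

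**2. Who stays in and who drops out.** Subjects who stop study drug but give the week-24 sample stay in, and sections 3.7.1, 3.7.3 and 3.8 aim for this. These subjects drop out:

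- those who die before the sample;
- those who leave and do not return;
- those followed only by the fallback routes in 3.8 (telephone, a practitioner or relative, or a single contact at study end), which can yield adverse event information but no HbA1c unless the subject also attends the final visit;
- wrongly enrolled subjects withdrawn under 3.4 after dosing, if no sample is taken.

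**3. The plan's own figures.** Section 8.1 gives a difference of 0.3, an SD of 1.0, 80% power and a 5% level. The sidedness is not stated; two-sided reproduces the result.

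- Normal approximation: n = 2 × (1.960 + 0.842)² × 1.0² / 0.3² = 174.4, so 175 per arm.
- t-test: 175.4, so 176 per arm, with power 0.801.
- Dropout: 176 / 0.90 = 195.6, so 196 per arm and 392 in total.

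The stated 176 and 392 reproduce.

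**4. Subjects outside the safety set.** 392 − 2 × 176 = 392 − 352 = 40, about 20 per arm (40/392 = 10.2%). This assumes that dropout in 8.1 means no week-24 HbA1c, which section 3.9 supports by defining loss to follow-up as incomplete ascertainment of the primary outcome. It also assumes that all 40 were dosed.

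**5. Effect on a tabulated rate.** Let p be the true risk of the event, m the share of the arm without the sample, and f the share of event subjects without the sample.

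Tabulated rate = p × (1 − f) / (1 − m)

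The protocol gives neither p nor f. Assume p = 5% and m = 10%. Then 196 × 0.05 = 9.8 event subjects, and 196 × 0.90 = 176.4 subjects remain in the set.

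| f | Event subjects kept | Tabulated rate |
|---|---|---|
| 0% | 9.80 | 5.6% |
| 10% | 8.82 | 5.0% |
| 25% | 7.35 | 4.2% |
| 50% | 4.90 | 2.8% |
| 75% | 2.45 | 1.4% |
| 100% | 0 | 0% |

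The break-even is f = m = 10%. Above it the rate is understated; below it the rate is slightly overstated. For deaths before the sample, f is 100% by definition, so the tabulated rate is 0 whatever the true rate.

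The result is not sensitive to m. At f = 50%, m = 5% gives 0.05 × 0.50 / 0.95 = 2.63%, and m = 15% gives 0.05 × 0.50 / 0.85 = 2.94%.

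**6. Unequal loss.** With a true 5% in both arms, m = 10% in both, f = 25% in one arm and 75% in the other, the table shows 4.2% against 1.4% (7.35 against 2.45 expected subjects). The ratio is 0.75 / 0.25 = 3, with no true difference.

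**The case against.** The strongest reply is that little should be lost in practice. The protocol presses for follow-up after drug discontinuation, HbA1c included, so stopping for an adverse event does not by itself remove a subject. Treatment lasts 24 weeks, and patients with ASCVD or a life expectancy under 6 months are excluded, so deaths may be few. Section 6.4.3 says that all collected adverse events will be summarised, so events outside the FAS should still appear somewhere in the report. Safety is not a primary or secondary endpoint. The statistical analysis plan may also define a proper safety set.

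Some of this stands. The defect lies in the by-arm incidence tables and their denominators; it does not mean that deaths vanish from the report. It applies to deaths before the sample, not to every death before week 24, because visit 4 has a window of ±7 days. Section 6.4.1 sets only the period of adverse event collection and does not contradict 8.3. The 5% risk and the 25% against 75% split have no source in the protocol; they show that distortion is possible, not that it is likely. The figure of 40 is a planning figure that actual loss may exceed or fall short of.

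None of it removes the rule. Section 6.4.3 gives no set or denominator, so it conflicts with 8.3 without replacing it. The choice of safety set is not left open for the analysis plan, because the protocol states it; an analysis plan that used all treated subjects would contradict the protocol.

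**Conclusion.** The concern holds and should be corrected before the analysis. Followed as written, 8.3 removes from the 8.4.3 tables every treated subject without a week-24 HbA1c, and so every subject who dies before that sample. This also conflicts with the promise in 6.4.3.

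On the protocol's own dropout figure, about 40 of 392 subjects are affected, fewer if some were never dosed. The direction of error for other events depends on whether subjects with the event lack the sample more or less often than the arm as a whole. The size in step 5 rests on assumed values. The exclusion itself follows from the text and needs no assumption. The primary HbA1c comparison does not depend on the use of this set for safety.

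**What to change.** Add to section 8.3 a safety set of all randomised subjects who took at least one dose of study drug, with no HbA1c condition. Name this set in 8.4.3 as the basis for all adverse event tables, including the subgroup tables. Change the sentence in 8.3 so that the FAS serves efficacy only.

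With this change the planned safety denominator is up to 392 (196 per arm) in place of about 352 (176 per arm).

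The cost is one added definition, one changed sentence and the name of the set in 8.4.3. No visit, sample or subject is added, since adverse events are already to be collected throughout the study under 6.4.1. Reported rates may move in either direction; they will rise where subjects with events are the ones more likely to miss the sample.
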